11.4. Appendix 4: Data Display Standards & Handling Conventions

11.4.1. Reporting Process

Software

 The currently supported versions of SAS software will be used to perform all data analyses, generate tables, figures and listings.

Reporting Area

| HARP Server | : us1salx00259 |
|---------------|---------------------------------------|
| HARP Compound | : \arprod\cci15106\mid205822\final_03 |

Analysis Datasets

- Analysis datasets will be created according to CDISC standards (AdaM IG Version 1.0).
- For creation of ADaM datasets (ADCM/ADAE), the same version of dictionary datasets will be implemented for conversion from SI to SDTM.

Generation of RTF Files

RTF files may be generated for SAC tables...

11.4.2. Reporting Standards

General

- The current GSK Integrated Data Standards Library (IDSL) will be applied for reporting, unless otherwise stated (IDSL Standards Location: https://spope.gsk.com/sites/IDSLLibrary/SitePages/Home.aspx):
 - 4.03 to 4.23: General Principles
 - 5.01 to 5.08: Principles Related to Data Listings
 - 6.01 to 6.11: Principles Related to Summary Tables
 - 7.01 to 7.13: Principles Related to Graphics

Formats

- All data will be reported according to the actual treatment the subject received unless otherwise stated.
- GSK IDSL Statistical Principles (5.03 & 6.06.3) for decimal places (DP's) will be adopted for reporting of data based on the raw data collected.
- Numeric data will be reported at the precision collected on the CRF.
- The reported precision from non CRF sources will follow the IDSL statistical principles but may be adjusted to a clinically interpretable number of DP's.

Planned and Actual Time

- Reporting for tables, figures and formal statistical analyses:
 - Planned time relative to dosing will be used in figures, summaries, statistical analyses and calculation of any derived parameters, unless otherwise stated.
 - The impact of any major deviation from the planned assessment times and/or scheduled visit days
 on the analyses and interpretation of the results will be assessed as appropriate.
- Reporting for Data Listings:
 - Planned and actual time relative to study drug dosing will be shown in listings (Refer to IDSL Statistical Principle 5.05.1).
 - Unscheduled or unplanned readings will be presented within the subject's listings.
 - Visits outside the protocol defined time-windows (i.e. recorded as protocol deviations) will be included in listings but omitted from figures, summaries and statistical analyses.

| Unscheduled Visits | | | | | | |
|---|--|--|--|--|--|--|
| Unscheduled visits | Unscheduled visits will not be included in summary tables. | | | | | |
| Unscheduled visits | Unscheduled visits will not be included in figures. | | | | | |
| All unscheduled visits will be included in listings. | | | | | | |
| Descriptive Summary Statistics | | | | | | |
| Continuous Data Refer to IDSL Statistical Principle 6.06.1 | | | | | | |
| Categorical Data N, n, frequency, % | | | | | | |
| Graphical Displays | | | | | | |
| Refer to IDSL Statistical Principals 7.01 to 7.13. and Standards for the Transfer and Reporting of PK Data using HARP | | | | | | |

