5.2. Baseline Definitions

5.2.1. Baseline Definitions

For all endpoints (except as noted in baseline definitions) the baseline value will be the latest pre-dose assessment.

For tabulated safety summaries, only the scheduled assessments will be included in the summary tables.

| Parameter | Study Assessn | Study Assessments Considered as Baseline | | | | | | | | | |
|----------------------------------|---------------|--|----------------------|------------------|--|--|--|--|--|--|--|
| | Screening | Day -1 | Day 1 (Pre- Dose) | in Data Display | | | | | | | |
| Safety | | | | | | | | | | | |
| 12 Lead ECG & Vital Signs | Х | - | Х | Day 1 (Pre-Dose) | | | | | | | |
| Spirometry | Х | - | X | Day 1 (Pre-Dose) | | | | | | | |
| Haematology/Chemistry/Urinalysis | Х | X | - | Day - 1 | | | | | | | |
| Telemetry | - | - | X | Day 1 (Pre-Dose) | | | | | | | |

NOTES:

 Unless otherwise stated, the mean of replicate assessments at any given time point will be used as the value for that time point.

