7.3. Clinical Laboratory Analyses

Laboratory results will be included in the reporting of this study for hematology, coagulation, clinical chemistry, and urinalysis.

Protocol-specified clinical laboratory tests will be summarized using descriptive statistics. The statistics will be presented for each scheduled assessment during the study and change from baseline to each scheduled assessment. Presentations will use SI Units, as provided by the labs or converted from values in other units. Clinical laboratory data collected during unscheduled visits of study conduct that were not required per protocol, such as for special testing to evaluate an AE, will be listed and not summarized.

Based upon laboratory normal ranges, the laboratory test results will be categorized according to the normal range as low (below the lower limit), normal (within the normal range) and high (above the upper limit). Summary statistics for change from baseline based on PCI will also be tabulated. The details of the planned displays are in Appendix 11: List of Data Displays.

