11.5. Appendix 5: Derived and Transformed Data

11.5.1. General

Multiple Measurements at One Analysis Time Point

- Mean of the measurements will be calculated and used in any derivation of summary statistics but if listed, all data will be presented.
- Subjects having both High and Low values for Normal Ranges at any post-baseline visits for safety
 parameters will be counted in both the High and Low categories of "Any visit post-baseline" row of
 related summary tables. This will also be applicable to relevant Potential Clinical Importance summary
 tables.

Study Day

- Calculated as the number of days from randomisation date:
 - Ref Date = Missing
 - → Study Day = Missing
 - Ref Date < Randomisation Date → Study Day = Ref Date Randomisation Date
 - Ref Date ≥ Randomisation Date → Study Day = Ref Date (Randomisation Date) + 1

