| 3.42. | Bystander Safety (Part 1, Cohort C) | EG2 | Summary of Change from Baseline in ECG Values by Visit – Bystander | Only for Cohort C, Part 1. | SAC |
| 3.43. | Safety | Non-standard SAFE_T7 | Frequency of Maximum ECG Values by PCI Category – Part 1 | Compute and display Maximum by day. | SAC |
| 3.44. | Safety | Non-standard SAFE_T7 | Frequency of Maximum ECG Values by PCI Category – Part 2 | | SAC |
| 3.45. | Bystander Safety (Part 1, Cohort C) | Non-standard SAFE_T7 | Frequency of Maximum ECG Values by PCI Category – Bystander | Compute and display Maximum by day. Only for Cohort C, Part 1. | SAC |
| 3.46. | Safety | Non-standard SAFE_T8 | Frequency of Worst Change from Baseline Values of QTcB and QTcF by PCI Category – Part 1 | Compute and display Maximum by day. | SAC |
| 3.47. | Safety | Non-standard SAFE_T8 | Frequency of Worst Change from Baseline Values of QTcB and QTcF by PCI Category – Part 2 | | SAC |
| 3.48. | Bystander Safety (Part 1, Cohort C) | Non-standard SAFE_T8 | Frequency of Worst Change from Baseline Values of QTcB and QTcF by PCI Category – Bystander | Compute and display Maximum by day. Only for Cohort C, Part 1. | SAC |
| Vital Si | gns | | | | |
| 3.49. | Safety | VS1 | Summary of Vital Signs by Visit – Part 1 | This will not include Cohort C, Part 1. | SAC |
| 3.50. | Safety | VS1 | Summary of Vital Signs by Visit – Part 2 | | SAC |
| 3.51. | Bystander Safety (Part 1, Cohort C) | VS1 | Summary of Vital Signs by Visit – Bystander | Only for Cohort C, Part 1. | SAC |

| Safety: | Safety: Tables | | | | | | | |
|---------|---|-------------------------|---|---|---------------------------|--|--|--|
| No. | Population | IDSL / Example Shell | Title | Programming Notes | Deliverable [Priority] | | | |
| 3.52. | Safety | VS1 | Summary of Change from Baseline in Vital Signs by Visit – Part 1 | This will not include Cohort C, Part 1. | SAC | | | |
| 3.53. | Safety | VS1 | Summary of Change from Baseline in Vital Signs by Visit – Part 2 | | SAC | | | |
| 3.54. | Bystander Safety (Part 1, Cohort C) | VS1 | Summary of Change from Baseline in Vital Signs by Visit – Bystander | Only for Cohort C, Part 1. | SAC | | | |
| 3.55. | Safety | VS2 | Summary of Vital Signs by PCI – Part 1 | This will not include Cohort C, Part 1. | SAC | | | |
| 3.56. | Safety | VS2 | Summary of Vital Signs by PCI – Part 2 | | SAC | | | |

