| | Worst Post Baseline | n Increase<=30 30 <increase<=60 increase="">60</increase<=60> | 12 12(100%) 0 | 6 6(100%) 0 | 6 6(100%) 0 |

Example SAFE_T7
Protocol: 205822
Population: Safety

rotocol: 205822 Page 1 of 1

Table X
Frequency of Maximum ECG Values by PCI Category

| ECG Test | Visit | Category | Placebo (N=12) | 1 capsule - Single Dose | Single Dose |
|------------------------------------|------------------------|--|-------------------------------|----------------------------|------------------------|
| PR Interval, Aggregate (msec) | BASELINE | n | 12 | 6 | 6 |
| nggregate (mete) | | Value<110 110<=Value<=220 Value>220 | | 0 6(100%) 0 | 0 6(100%) 0 |
| | WORST POST BASELINE | n Value<110 110<=Value<=220 Value>220 | - | 6 0 6(100%) 0 | 6 0 6(100%) 0 |
| QRS Duration, Aggregate (msec) | SCREENING | n | 12 | 6 | 6 |
| 1199209000 (111000) | | Value<75 75<=Value<=110 Value>110 | , , | 0 6 (100%) 0 | 0 6(100%) 0 |
| | WORST POST BASELINE | n Value<75 75<=Value<=110 Value>110 | 12 0 11 (92%) 1 (8%) | 6 0 6(100%) 0 | 6 0 6(100%) 0 |
| QTcB Interval, Aggregate (msec) | SCREENING | n | 12 | 6 | 6 |

205822

| | Value<=450 | 11 (92%) | 6 (100%) | 6 (100%) |
|------------|--|----------|----------|----------|
| | 450 <value<480< td="">1 (8%)	0	0	</value<480<> | 1 (8%) | 0 | 0 |
| | 480<=Value<500 | 0 | 0 | 0 |
| | Value>=500 | 0 | 0 | 0 |
| WORST POST | n | 12 | 6 | 6 |
| BASELINE | Value<=450 | 11 (92%) | 5 (83%) | 6 (100%) |
| | 450 <value<480< td="">1 (8%)	1 (17%)	0	</value<480<> | 1 (8%) | 1 (17%) | 0 |
| | 480<=Value<500 | 0 | 0 | 0 |
| | Value>=500 | 0 | 0 | 0 |

Repeat for QTcF

Note: Percentages may not add up to 100 for QRS Duration and PR Interval as there is a possibility of a patient being counted under both low and high categories.

205822

Example : PK_T1 Page 1 of n : 205822

Population : Systemic PK

Table 3.1.13
Summary of Assessment of Dose Proportionality (Part 1 and Part 2)

| | | | Slope | | | _ | | | |
|-----------|-------|---|----------|----|--------|----------|----|--------|----------------|
| Parameter | Study | n | Estimate | SE | 90% CI | Estimate | SE | 90% CI | Coefficient of |
| | Day | | | | | | | | Determination |

Note(s): CI = confidence interval; SE = standard error.

Source: SAS Output XX

205822

Example : PK_T2 Page 1 of n

Protocol : 205822 Population : Systemic PK

Table 3.1.16 Summary of Assessment of Steady State (Part 1 and Part 2)

| | | | Slope | Slope | | | | |

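### Unscheduled values are excluded even from the worst and any-visit post-baseline rows, so those rows can under-count participants with values of potential clinical importance, chiefly laboratory values

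*SAP*

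**What the plan says.** The exclusion is stated three times in the SAP:

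- Section 11.4.2, on unscheduled visits: "Unscheduled visits will not be included in summary tables". They are also kept out of figures, and the place left for them is the listings: "All unscheduled visits will be included in listings".
- Section 5.2.1, for safety in particular: "For tabulated safety summaries, only the scheduled assessments will be included in the summary tables".
- Section 7.3, for laboratory data from unscheduled visits that the protocol did not require: "such as for special testing to evaluate an AE, will be listed and not summarized".

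The SAP also plans rows that cover the whole post-baseline period:

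- Section 11.5.1 has the rule "Subjects having both High and Low values for Normal Ranges at any post-baseline visits for safety", which continues "parameters will be counted in both the High and Low categories of 'Any visit post-baseline' row of" the related tables. Its next sentence extends the rule to the relevant PCI tables.
- The ECG mock shells in section 11.11 carry a row labelled "Worst Post Baseline". They serve displays such as "Frequency of Maximum ECG Values by PCI Category" (Tables 3.43 to 3.45) and the tables of worst QTc change from baseline (3.46 to 3.48).

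No section says that these rows draw on a different set of records from the by-visit rows.

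**The concern.** Restricting by-visit means to scheduled assessments is ordinary practice, because an unscheduled reading belongs to no planned time point. A worst or any-visit row answers a different question: did this participant ever cross the threshold after baseline? Read with the exclusion, its label means worst scheduled or any scheduled visit, and nothing in the shells shown says so.

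Safety and tolerability is the first primary objective (section 2.2) and no hypothesis is tested (section 2.4), so these descriptive tables carry much of the safety conclusion. The exclusion also differs in spirit from the adverse event rules in section 7.2. There, missing severity is taken as severe, missing relationship as related, and uncertain emergence as treatment emergent.

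**Working it through.** The SAP gives no figure to reproduce. The check compares the rules, then works out direction and size.

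**1. Reach of the rule.** Sections 5.2.1, 7.3 and 11.4.2 bear on tables built from assessments: laboratory, ECG, vital signs, spirometry and telemetry. Adverse event tables (3.1 to 3.18) and exposure tables (3.58 to 3.60) are not built from visit assessments and are untouched.

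**2. Rows at issue.**

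| Domain | PCI tables | Basis for a whole-period row |
|---|---|---|
| ECG | 3.43–3.48 | Worst post-baseline row printed in the shells |
| Chemistry, haematology | 3.22–3.24, 3.28–3.30 | Inferred from section 11.5.1; the LB17 shell is not shown |
| Vital signs | 3.55–3.57 | Inferred from section 11.5.1; the VS2 shell is not shown |

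For Tables 3.43, 3.45, 3.46 and 3.48 the programming note asks for the maximum by day, while the shells show one worst post-baseline row. The two instructions are not reconciled. (Tables 3.46 to 3.48 cite shell SAFE_T8; the shell with that title is labelled SAFE_T6.)

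**3. Direction.** For one participant, let S be the scheduled and U the unscheduled post-baseline values.

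- max(S) ≤ max(S ∪ U), and for a low threshold min(S) ≥ min(S ∪ U).
- So the number of participants at or beyond any threshold, counted on S, is at most the number counted on S ∪ U.
- A participant is lost from a category only if some value in U meets it and no value in S does. If a scheduled value already qualifies, nothing changes.

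For example, section 11.7.1 flags a haemoglobin fall of more than 25 g/L from baseline. A participant in a BID cohort who crosses that limit only on an unscheduled sample between Days 7 and 15 would be listed but not counted.

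**4. Size per participant.** The change in a rate is 1/N, provided the participant has at least one scheduled post-baseline value and so stays in the denominator. The mock shells show N=12 for Part 1 Cohort B and N=4 for pooled Part 1 placebo; these sizes are assumptions.

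- N=12: 1/12 = 8.3 percentage points.
- N=4: 1/4 = 25 percentage points.

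The number of such participants cannot be known from the SAP and may be zero.

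**5. Where an unscheduled test is most likely to be the only evidence** (section 11.2.1, assessments after dosing starts).

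| Assessment | Days |
|---|---|
| Laboratory, 14-day BID cohorts | 7, 15, follow-up |
| Laboratory, Part 2 Cohort A | 2, follow-up |
| Laboratory, Part 1 Cohort A | 2, 5, 12, 22, follow-up |
| ECG and vital signs, 14-day BID cohorts | 1, 3, 4, 6, 7, 8, 10, 12, follow-up |

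**6. Backstop.** Listings 55–57 (ECG) and 65–67 (vital signs) show all values for any participant with a PCI value. Laboratory data are listed in full (38–48), but no listing picks out participants with laboratory PCI values. Laboratory data therefore combine the sparser schedule with the weaker backstop.

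**The case against.** The other side has a good deal to say, and most of it limits the reach of the point without removing it.

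- **The rule is prespecified and consistent.** This stands: the three statements agree. The defect is that they make no exception where one is needed.
- **Nothing is lost.** Every unscheduled value is listed, groups of 4 to 12 can be read by eye, and an adverse event that prompted a test is itself tabulated if treatment emergent. This stands, and it is why the matter is moderate. A reader who relies on the PCI table would still see a worst or any-visit count that is incomplete without being labelled so.
- **The schedule argument does not carry to every table.** This stands. Nine of the 15 PCI tables concern ECG or vital signs, which are measured often, and Part 1 Cohort A has more laboratory days than the BID cohorts.
- **The affected rows are not all shown.** This stands for LB17 and VS2, because section 11.5.1 speaks only of relevant PCI tables.

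A reader might infer that the safety tables do under-count, or that unscheduled readings are the most extreme ones. The SAP supports neither: the loss is conditional, and nothing in the SAP shows how extreme unscheduled readings will be. Nor can one infer a bias between active treatment and placebo. The filter applies to all groups, so only the direction in each group's count is fixed.

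**Conclusion.** The point holds in a conditional form. As written, worst and any-visit post-baseline rows exclude unscheduled values, so they can under-count participants whose only or worst PCI value was unscheduled. Any error in the number reaching a threshold is downward. It is zero if no such value occurs, and each affected participant moves a rate by 1/N, as illustrated above. It should not be read as a fault in all safety tables.

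The conclusion rests on two assumptions: that the LB17 and VS2 displays contain the any-visit row that section 11.5.1 describes, and that the final group sizes resemble those in the mock shells. The priority is laboratory PCI. The change is worth making because it is cheap and makes the rows mean what their labels say.

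**What to change.** 1. Keep by-visit and by-day summaries restricted to scheduled assessments.
2. State in section 11.4.2 that any worst post-baseline or any-visit post-baseline row in the laboratory, ECG and vital-sign normal-range and PCI tables uses all post-baseline values, scheduled and unscheduled. Where such rows are produced, this covers Tables 3.22–3.24, 3.28–3.30, 3.43–3.48 and 3.55–3.57.
3. Align sections 5.2.1 and 7.3 with that sentence, so that laboratory tests done to evaluate an adverse event stay out of by-visit statistics but count in these rows.
4. Reconcile the maximum-by-day note for Tables 3.43, 3.45, 3.46 and 3.48 with the worst post-baseline row in the shells.

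The cost is SAP wording and a changed record filter for the affected rows, with no new data collection and no change to by-visit results. The downside is that PCI counts may look slightly less favourable.

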11.4.3. Reporting Standards for Pharmacokinetic

| Pharmacokinetic Con | Pharmacokinetic Concentration Data | | | | | | |
|---|--|--|--|--|--|--|--|
| PC Windows Non- Linear (WNL) File | PC WNL file (CSV format) for the non compartmental analysis by Clinical Pharmacology Modelling and Simulation function will be created according to [Insert document name]. Note: Concentration values will be imputed as per GUI_51487 | | | | | | |
| Descriptive Summary Statistics, Graphical Displays and Listings | Refer to IDSL PK Display Standards. Refer to IDSL Statistical Principle 6.06.1. Note: Concentration values will be imputed as per GUI_51487 for descriptive summary statistics/analysis and summarized graphical displays only. | | | | | | |
| Pharmacokinetic Parameter Data | | | | | | | |
| Descriptive Summary Statistics (Log Transformed) | N, n, geometric mean, 95% CI of geometric mean, standard deviation (SD) of log-transformed data and between geometric coefficient of variation (CVb (%)) will be reported. [1] CV_b (%) = $\sqrt{\exp(SD^2) - 1}$ * 100 (SD = SD of log transformed data) | | | | | | |
| Parameters Not Being Log Transformed | N, n, geometric mean, 95% CI (Lower, Upper), standard deviation (SD), median, minimum and maximum | | | | | | |
| Listings | Interval, number of observations included in calculation of lambda_z, regression coefficient and percent AUC extrapolated (%AUCex) | | | | | | |

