2.3. Study Design

2.4. Statistical Hypotheses

The primary objective of the study is to investigate the safety and tolerability of CCI15106-IP following single and repeat escalating doses in healthy participants and participants with moderate COPD. No statistical hypotheses will be tested.

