3.2. Final Analyses

Safety and PK analyses are the primary statistical analyses for this study.

Data will be listed and summarized according to GSK reporting standards, where applicable. All the displays will be split by part. Study population tables would be presented by cohort and a combined placebo (of all cohorts with the exception of Part 1, Cohort C (bystanders)). For Safety displays, listings will be sorted by dose, participant and time; summaries will be presented by dose and time for different parts of the study. Participants receiving placebo may be combined into one treatment group in the summaries within each part.

Descriptive summaries will include n, mean, standard deviation (SD), median, minimum, and maximum, geometric mean with associated 95% confidence interval (CI), and the between-participant coefficient of variation (%CVb) for continuous variables related to PK parameters, n and percent will be used as summary statistics for categorical variables.

Version 9.4 or higher of the SAS system will be used to analyse the data as well as to generate tables, figures, and listings.

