8.1.2.2. Statistical Analysis of Pharmacokinetic Parameters

Geometric mean will be included for PK parameters, wherever applicable.

The following PK statistical analyses will only be performed, if sufficient data is available (i.e. if participants have well defined plasma profiles).

Pharmacokinetic Statistical Analyses

Endpoint(s)

- All endpoints, except tmax and %AUCex, will be natural-log transformed prior to the analysis
- Dose Proportionality: AUC₍₀₋₂₄₎ or AUC₍₀₋₄₈₎, or AUC_(0-τ) and Cmax, for single dose and repeat dose of Part 1
- Steady State Assessment in BID dosing: Ctrough (using pre-dose concentration from day 6 in Cohort A Part 1, and day 2 onwards in Cohorts B, Part 1 and Part 2)
- Accumulation in BID dosing: accumulation ratio will be calculated for AUC_(0-τ) as [AUC_(0-τ), on Day 19/AUC_(0-τ), on Day 6 for Cohort A in Part 1, or AUC_(0-τ) on Day 14/AUC_(0-τ) on Day 1 for Cohorts B of both Part 1 and Part 2, from the ANOVA model

Model Specification

Dose Proportionality will be assessed separately by means of power model: y = α*dose^β where y
denotes the PK parameter being analyzed. PK parameters will be normalized to 60mg dose and then
log transformed prior to analysis

If the power model does not show dose proportionality then pairwise analysis of variance (ANOVA) may be used as an exploratory analysis to understand the dose where dose proportionality fails

- Analysis of variance (ANOVA), considering study Day as fixed effect and subject as a random effect in
 the model, will be performed using SAS Mixed Linear Models procedure to evaluate in the assessment
 of steady state in models included at least 3 days of pre-dose concentrations (like Days 4,6,8; Days
 6,8,10, Days 10,12,14 relative to first dose of repeat dosing). This will be done for each of the repeat
 dose treatments.
- Analysis of variance (ANOVA), considering study Day as fixed effect and subject as a random effect in
 the model, will be performed using SAS Mixed Linear Models procedure to evaluate in the assessment
 accumulation, where geometric least squares mean ratio of AUC_(0-τ) on Day 19/AUC_(0-τ) on Day 6 for
 Cohort A in Part 1, AUC_(0-τ) on Day 14/AUC_(0-τ) on Day 1 for Cohorts B and 90% CI will be calculated.

Note: Subjects will be fit as a fixed effect for the assessment of accumulation if the model fails to converge.

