- 10. PK samples on days 1, 3, 6, and 19 will be collected at the following timepoints: pre-dose, 0.25, 0.5, 0.75, 1, 2, 4, 6, 8, 10, 12 h. On day 2, one sample in the morning (24h post day 1 dose). On days 4 and 5, one sample on each morning (24h and 48h post day 3 dose). On days 6 and 19, the evening dose will be given after 12 h post-dose sample is collected. On all other days, PK sample will be collected once, before the morning dose (if on dosing days).

Schedule for Cohort A Part 2 (and all other single dose administrations)

| | Treatment Period, Days (D) and hours (h) | | | | | | | | | | | | | |
|---|--|---|----|-------|------|-------|----|----|----|----|----|-----|-----|-----------------|
| | D-1 D1 | | | | | | | | | | | | | D2 |
| Procedure | | Pre- dose | 0h | 0.25h | 0.5h | 0.75h | 1h | 2h | 4h | 6h | 8h | 10h | 12h | 24h |
| Inclusion and exclusion criteria | Х | | | | | | | | | | | | | |
| Brief physical examination, oral examination | X | | | | | | | | | | | | | Х |
| Substance testing (drugs, alcohol) | X | | | | | | | | | | | | | |
| Serum pregnancy test in women | X | | | | | | | | | | | | | |
| Admittance to clinic | X | | | | | | | | | | | | | |
| Inhaler device training ¹ | Х | | | | | | | | | | | | | |
| Randomization | Х2 | | | | | | | | | | | | | |
| Discharge | | | | | | | | | | | | | | Х3 |
| Haematology, clinical chem and urinalysis (include liver chem)4 | X | | | | | | | | | | | | | Χ |
| Spirometry | | X5 | | X6 | Χ | | Χ6 | | X6 | | | | | |
| Telemetry | | 30 min pre-dose and continuous until at least 4 h | | | | | | | | | | | | |
| 12-lead ECG and vital signs | | XXX | | X | | | Χ | X | X | | Χ | | Χ | |
| CCI15106-IP or placebo treatment | | | Х | | | | | | | | | | | |
| PK blood sample ⁷ | | Х | | Х | X | X | Х | Х | Х | Χ | Х | Х | X | Х |
| AE review | ← | | | | | | | | | | | | | |
| SAE review | (| | | | | | | | | | | | | |
| Concomitant medication review | (====== | | | | | | | | | | | | | > |

- 1. Day -1 inhaler training may be done on Day 1 instead, before the first dose administration. Other time-points may be added per investigators discretion
- 2. Can be performed on Day 1 prior to dosing
- 3. After all assessments are completed
- 4. To be drawn fasting (for at least 8 h)
- 5. To be performed within 15 to 60 minutes pre-dose
- 6. To be performed after ECG, VS and PK blood draw are obtained
- 7. Additional PK collection time points may be added to better characterize the PK profile

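### SAP 11.4.3 summarises PK parameters that are not log-transformed (in practice tmax) by a geometric mean with an unlabelled 95% CI and SD, and omits the arithmetic mean that section 3.2 lists

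*SAP*

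**What the plan says.** Section 11.4.3 of the SAP has two rows of descriptive statistics for PK parameters.

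- Log-transformed parameters: "N, n, geometric mean, 95% CI of geometric mean, standard deviation (SD) of log-transformed data and between geometric coefficient of variation", with the formula for that coefficient of variation. The target of the CI and the scale of the SD are both stated.
- Parameters that are not log-transformed: "N, n, geometric mean, 95% CI (Lower, Upper), standard deviation (SD), median, minimum and maximum". Here neither the target of the CI nor the scale of the SD is stated, and no arithmetic mean appears.

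Section 8.1.2.2 is the only place that says which parameters stay untransformed: "All endpoints, except tmax and %AUCex, will be natural-log transformed prior to the analysis". The same section adds: "Geometric mean will be included for PK parameters, wherever applicable".

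Section 3.2 gives the general rule for PK parameters, which includes the arithmetic mean: "Descriptive summaries will include n, mean, standard deviation (SD), median, minimum, and maximum, geometric mean with associated 95% confidence interval (CI".

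tmax is among the primary PK endpoints in section 2.2, is derived after single and repeat dosing (Tables 5 and 6), and falls under Table 4.4, the summary of derived plasma PK parameters. %AUCex is in neither Table 5 nor Table 6; section 11.4.3 names it only under listings ("Interval, number of observations included in calculation of lambda_z, regression coefficient and percent AUC extrapolated (%AUCex").

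**The concern.** The geometric mean is the exponential of the mean of the logs. To prescribe it for parameters defined as not log-transformed is to ask for the calculation that the row heading rules out. Beside it stand an SD that reads as raw-scale and a CI with no named target. A programmer following the row could attach the interval to either mean, or could combine the geometric mean with the raw SD, which gives an interval belonging to neither.

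The row also disagrees with section 3.2 on whether an arithmetic mean is reported at all. At stake is whether the tabulated centre, SD and interval for tmax can be read together, and whether two programmers would produce the same table.

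**Working it through.** The plan states no figure on this point, so there is nothing to reproduce. The check has two parts.

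**1. The passages side by side**

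| Item | 11.4.3, log-transformed | 11.4.3, not log-transformed | 3.2, PK parameters |
|---|---|---|---|
| Arithmetic mean | no | no | yes |
| Geometric mean | yes | yes | yes |
| 95% CI | of the geometric mean | target not stated | of the geometric mean |
| SD | of log data | scale not stated | scale not stated |
| Between-subject CV | yes | no | yes |
| Median, min, max | no | yes | yes |

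The untransformed row drops the log-scale labels and the CV and adds the median and range. Every change from the row above moves towards the raw scale; only the geometric mean remains from the log scale.

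**2. How far apart the statistics can be**

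Inputs: the tmax values are assumed. They are placed on the plan's sampling times ("pre-dose, 0.25, 0.5, 0.75, 1, 2, 4, 6, 8, 10, 12 h"), with n = 6 or 12 for illustration.

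Formulas: AM = Σx/n; GM = exp(Σ ln x / n); raw-scale CI = AM ± t·SD/√n; log-scale CI = GM × exp(± t·SD_ln/√n), with t on n − 1 degrees of freedom.

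| Assumed tmax (h) | AM | GM | Median | GM/AM |
|---|---|---|---|---|
| 0.5 ×5, 0.75 | 0.542 | 0.535 | 0.500 | 0.988 |
| 0.25, 0.25, 0.5, 0.5, 0.75, 1 | 0.542 | 0.477 | 0.500 | 0.880 |
| 0.25 ×3, 0.5 ×4, 0.75 ×2, 1 ×2, 2 (n = 12) | 0.688 | 0.567 | 0.500 | 0.824 |
| 0.25, 0.5, 0.5, 0.75, 1, 2 | 0.833 | 0.674 | 0.625 | 0.809 |
| 0.25, 0.25, 0.5, 0.5, 1, 2 | 0.750 | 0.561 | 0.500 | 0.748 |

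The geometric mean is therefore 1% to 25% below the arithmetic mean in these sets. For a lognormal variable GM/AM = 1/√(1 + CV²): 0.98 at CV 20%, 0.89 at CV 50% and 0.71 at CV 100%.

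The last set in full (n = 6, t = 2.571):

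- AM = 4.5/6 = 0.75 h. The squared deviations sum to 2.25, so SD = √(2.25/5) = 0.671 h.
- GM = (0.25 × 0.25 × 0.5 × 0.5 × 1 × 2)^(1/6) = 0.03125^(1/6) = 0.561 h; SD_ln = 0.810.
- Raw-scale half-width: 2.571 × 0.671/2.449 = 0.704, so the CI is 0.05 to 1.45 h around the AM.
- Log-scale half-width: 2.571 × 0.810/2.449 = 0.850, so the CI is 0.24 to 1.31 h around the GM.
- Mixed, GM ± raw half-width: 0.561 ± 0.704 gives −0.14 to 1.27 h, a negative lower limit for a time.

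The fourth set gives 0.18 to 1.49 h (raw), 0.32 to 1.42 h (log) and 0.02 to 1.33 h (mixed). The row as worded does not say which of the three is meant.

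**The case against.** The strongest case on the other side is that little is lost.

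- **The arithmetic mean is not absent from the plan.** Section 3.2 lists it for PK parameters. This stands: the omission is in the 11.4.3 row, and the defect is a conflict between two sections.
- **The exemption in 8.1.2.2 concerns transformation before statistical analysis.** It does not in itself forbid a descriptive geometric mean, and the same section allows one where applicable. This stands as far as it goes, but 11.4.3 settles applicability by prescribing a geometric mean for the untransformed class, and still leaves the CI and SD undefined.
- **The row already gives the median, minimum and maximum**, which is the more useful summary for tmax. This stands and limits the harm.
- **Table 4.4 uses a standard shell that is not reproduced in the SAP**, so its final content cannot be seen. True, but section 11.4.3 is the written instruction.

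Three stronger readings are tempting, and the documents do not support them. A reader might infer that the reported centre is biased low. It is lower only relative to the arithmetic mean; in all five sets above the geometric mean is closer to the median than the arithmetic mean is, and in four of them it exceeds the median. A reader might infer that extrapolation will look smaller than it is because %AUCex is summarised this way. Nothing says that %AUCex will be summarised. A reader might take it as stated that the SD is raw, or as certain that the authors meant the arithmetic mean. Both are natural inferences from the missing labels, but the SAP states neither.

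**Conclusion.** The row is wrong as written. It prescribes a log-scale centre for parameters that are not log-transformed, omits the arithmetic mean listed in section 3.2, and leaves the target of the CI and the scale of the SD open. For tmax, the gap between geometric and arithmetic mean is about 1% to 25% over the assumed sets. The direction always holds; the size depends on the spread, which the SAP does not give. The mismatch of scales rests on reading the SD as untransformed.

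The reach is small. The effect is on the descriptive summary in Table 4.4. Section 2.4 says "No statistical hypotheses will be tested", and tmax does not enter the dose-proportionality, steady-state or accumulation analyses, so no AUC or Cmax result changes. %AUCex is affected only if it is summarised; in that case a single zero would also make its geometric mean zero.

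**What to change.** In section 11.4.3, row *Parameters Not Being Log Transformed*, replace the geometric mean, the unlabelled CI and the unlabelled SD with: arithmetic mean, 95% CI of the arithmetic mean, SD of the untransformed data. Keep N, n, median, minimum and maximum, and state that median and range are the main summary for tmax.

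Align section 3.2 by saying that the geometric mean, its CI and the between-subject CV apply to log-transformed parameters only. Name tmax in the row, and %AUCex as well if it is to be summarised and not only listed.

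The cost is one table row and one sentence in the SAP, plus a check that the shell for Table 4.4 matches. No new data are needed and no other analysis changes.
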